2.2 Implementation outcomes

The SAT2HIV-II Project's four implementation outcomes are:

MIBI implementation consistency: The cumulative number of MIBIs that each MIBI staff member implemented during the implementation phase.

MIBI implementation quality: The cumulative sum quality score that each MIBI staff member demonstrated during the implementation phase. Each MIBI session will be rated using the Lyssn Platform and the Independent Tape Rater Scale.⁶³

MIBI sustainment consistency: The cumulative number of MIBIs that each MIBI staff member implemented during the sustainment phase.

MIBI sustainment quality: The cumulative sum quality score that each MIBI staff member demonstrated during the sustainment phase. Only the Lyssn Platform will be used to rate each MIBI session during the sustainment phase.

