2 OBJECTIVES & OUTCOMES

2.1 Objectives

The objective of the SAT2HIV-II Project is to test the effectiveness of P4P in improving implementation, sustainment, and client outcomes. Specific aims and hypotheses are:

Primary aim: Test the impact of ATTC+ISF+P4P on *implementation outcomes*.

Primary hypothesis: Relative to ATTC+ISF, ATTC+ISF+P4P will achieve significant improvements in staff-level measures of MIBI implementation consistency, MIBI implementation quality, MIBI sustainment consistency, and MIBI sustainment quality.

Secondary aim: Test the impact of ATTC+ISF+P4P on *client outcomes*.

Secondary hypothesis: Relative to ATTC+ISF, ATTC+ISF+P4P will achieve significant reductions in client-level measures of substance use, anxiety symptoms, and depression symptoms.

Exploratory aim: Test the extent to which implementation climate mediates the implementation condition to outcome relationship.

Exploratory hypothesis: Implementation climate will partially mediate the relationship between implementation condition and each of the outcomes in the primary and secondary aims.

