3.1 HSO staff

Each collaborating HSO will select their staff to be invited to participate as part of the project. Staff may participate as leadership staff or as MIBI staff.

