4.2 HSO clients

During the project's implementation phase, we will seek to inform all HSO clients who have been diagnosed with HIV and are 18 years of age or older about the research project. A copy of the project's participant recruitment flyer will be included as part of the collaborating HSOs' pre-appointment paperwork and posted on the HSOs' bulletin boards and websites. Interested individuals may access the online informed consent via their own internet-capable device or, as described on the recruitment flyer, they may request to use one of the project's electronic tablets. As noted on the recruitment flyer and in the informed consent, individuals may call the project's toll-free number (to be determined) or email the project's email address ([contact]) with any questions or concerns they have about the project, both of which are monitored by the project's RTI-based research staff.

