5.2 HSO clients

The expected duration of participation for each HSO client participant is about 1 day if the MIBI is not recommended based on their answers on the initial assessment or about 5 weeks if the MIBI is recommended. All online client assessments will be programmed using Voxco. For all online client assessments, client participants will access them either via a unique link that is emailed to them or by entering a unique participant ID that is emailed to them.

Complete initial assessment. All consenting client participants will be asked to complete an online initial client assessment, which will take about 10 minutes to complete. Each client participant who completes the initial client assessment will receive \$10 as compensation.

Participate in a MIBI session. Client participants for whom the MIBI is recommended will be asked to participate in a 15-30-minute MIBI session with one of the project's trained MIBI staff, which will be recorded for quality assurance purposes.

Complete pre-MIBI assessment. Client participants who participate in a MIBI session will be asked to complete an online pre-MIBI client assessment, which will take about 20 minutes to complete, immediately prior to receiving the MIBI session. Each client participant who completes the pre-MIBI client assessment will receive \$20 as compensation.

Complete post-MIBI assessment. Immediately after receiving the MIBI session, client participants will be asked to complete an online post-MIBI client assessment, which will take about 10 minutes to complete. Each client participant who completes the post-MIBI client assessment will receive \$10 as compensation.

Complete 4-week follow-up assessment. Four weeks after receiving the MIBI session, client participants will be asked to complete an online follow-up client assessment, which will take about 10 minutes to complete. Each client participant who completes the follow-up client assessment will receive \$10 as compensation. Client participants who complete the follow-up client assessment within 24 hours of being emailed their unique link will receive \$10 in bonus compensation. Client participants who complete the follow-up client assessment within 48 hours of being emailed their unique link will receive \$5 in bonus compensation.

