10 DATA ANALYSIS PLAN

All analyses will follow the intent-to-treat principle and will be conducted using R, SAS, or Mplus. The distribution of each outcome will be examined before analysis. If a distribution exhibits sufficient nonnormality, we will consider other distributions as an alternative to the normal distribution. Doing so will yield more accurate standard errors and p-values. To assess whether distributional choices were appropriate, we will conduct residual diagnostics. Before fitting mixed effects regression models, we will examine variance partitioning between the levels. Intraclass correlations (ICCs) will be estimated and included in publications. Organized by aim, below are descriptions of the sample size, missing data, power, and analysis plan.

Primary Aim. Analyses on the impact of the P4P strategy (i.e., ATTC+ISF+P4P compared to ATTC+ISF) on staff-level outcomes will be analyzed using a three-level mixed-effects regression model (repeated-measures t nested in staff s nested in organization o) with an appropriate distributional assumption. The primary predictor will be the P4P indicator (an organization-level predictor), and its estimated effect is β_2 . Random intercepts β_{0so} will adjust for organization differences. Random slopes β_{1so} allow for change over time. The basic reduced form of the model is $y_{tso} = \beta_{0so} + \beta_{1so}Time + \beta_2P4P + \epsilon_{tso}$. This model will be generalized with a link function if the outcome y_{tso} is nonnormal. Model comparisons will be used to select an appropriate trajectory shape (e.g., linear, quadratic) for the *Time* variable. A sensitivity analysis will

be conducted for each outcome by adding potential staff-level confounders (e.g., sex, race) to the model.

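### Both MIBI consistency outcomes are counts per staff member with no allowance for client flow or staff numbers, which costs precision and leaves the contrast open to staffing that responds to allocation

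*Combined protocol and SAP*

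**What the plan says.** Section 2.2 defines implementation consistency as "The cumulative number of MIBIs that each MIBI staff member implemented during the implementation phase" and sustainment consistency as "The cumulative number of MIBIs that each MIBI staff member implemented during the sustainment phase". Neither has a denominator. Section 2.1 tests them at staff level: the primary hypothesis is of "significant improvements in staff-level measures of MIBI implementation consistency" and of three companion measures.

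Opportunity to deliver comes from two places:

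- **Clients.** Under section 4.2 clients come forward through a flyer, paperwork or postings, and consent online. Section 5.2 then says "Client participants for whom the MIBI is recommended will be asked to participate in a 15-30-minute MIBI session". The initial assessment thus identifies the clients for whom a MIBI is recommended. Recruitment is described for one phase only: "During the project's implementation phase, we will seek to inform all HSO clients who have been diagnosed with HIV".
- **Staff.** Section 3.1 says "Each collaborating HSO will select their staff to be invited to participate as part of the project". No minimum, maximum or selection date relative to randomization is given.

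The Primary Aim model in section 10 has Time and the P4P indicator as predictors, with random intercepts and slopes. Its sensitivity analysis consists of "adding potential staff-level confounders (e.g., sex, race) to the model". Caseload, recommended clients and staff numbers do not appear. Section 1.2 gives 30 cluster-randomized sites and a bonus paid to MIBI staff for each MIBI.

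**The concern.** A count with no denominator mixes willingness to deliver with opportunity to deliver. A staff member who sees 4 of 4 recommended clients scores below one who sees 10 of 40, although the first reached 100% and the second 25%.

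Two consequences matter for the primary aim. First, client flow per staff member differs between organizations, and P4P is assigned at that level. Unexplained variation there goes into the standard error of the P4P effect, and 30 organizations leave little room to absorb it. Second, the number of MIBI staff divides the outcome, each organization chooses it, and the plan does not require it to be fixed before allocation is known. If it changed because of allocation, the per-staff contrast would no longer follow what the organizations delivered.

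**Working it through.** **No plan figure to reproduce.** Section 10 announces descriptions of sample size and power, but none follow. The documents give no expected counts, staff numbers, ICC or standard deviation. Everything below except the 30 sites is assumed, including 15 organizations per arm.

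**1. Direction.** Mean count per staff member = clients recommended × proportion receiving a MIBI ÷ MIBI staff. Assume a fixed pool of 60 recommended clients and 40% uptake.

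- Two staff: 60 × 0.4 / 2 = 12.0 each (total 24).
- Three staff and 20% more delivered: 60 × 0.4 × 1.2 / 3 = 9.6 each (total 28.8).

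The total rises 20% and the outcome falls 20%.

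**2. How much of the count reflects flow.** On the log scale the flow share of between-organization variance is log(1+CVf²) / [log(1+CVf²) + log(1+CVd²)], where f is eligible clients per staff member and d is the proportion delivered.

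- CVf 0.2, CVd 0.4: 0.0392 / (0.0392 + 0.1484) = 21%.
- Equal CVs: 50%.
- CVf 0.8, CVd 0.2: 0.4947 / (0.4947 + 0.0392) = 93%.

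**3. Bias.** Null simulation, 4,000 trials, no P4P effect on delivery. Inputs: median 80 eligible clients per organization (CV 0.5), mean delivery 0.4 (SD 0.1), on average 3 staff, and a t test on the log of total per staff member.

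- Staffing unrelated to arm: rejection rate 5.1%, mean ratio 1.00.
- P4P arm averaging one more staff member (4 instead of 3): mean ratio 0.74, rejection rate 18%.

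**4. Precision.** Let log flow have SD σf (0.3, 0.5 or 0.7) and residual log delivery SD σe (0.3 or 0.5). Staff numbers are 2 to 5, equally likely, so the variance of log staff is s² = 0.117. The log mean count has variance V0 = σf² + s² + σe². The covariate is log(caseload / staff), where log caseload has SD σf and correlation r with true log flow. After adjustment the variance is V1 = V0 − (rσf² + s²)² / (σf² + s²), and the proportional fall in the standard error is 1 − √(V1/V0).

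| σf | σe | V0 | V1, r = 0.5 | SE fall | V1, r = 0.7 | SE fall |
|---|---|---|---|---|---|---|
| 0.3 | 0.3 | 0.297 | 0.170 | 24% | 0.140 | 31% |
| 0.3 | 0.5 | 0.457 | 0.330 | 15% | 0.300 | 19% |
| 0.5 | 0.3 | 0.457 | 0.297 | 19% | 0.225 | 30% |
| 0.5 | 0.5 | 0.617 | 0.457 | 14% | 0.385 | 21% |
| 0.7 | 0.3 | 0.697 | 0.481 | 17% | 0.348 | 29% |
| 0.7 | 0.5 | 0.857 | 0.641 | 13% | 0.508 | 23% |

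A simulation of the same regression with 30 organizations (4,000 trials per row and value of r) gave falls of 12% to 30%, slightly smaller because a covariate is estimated. The formula leaves out Poisson variation in the counts, which would shrink the gain further where counts are small. Part of the gain comes from knowing the staff number exactly.

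**The case against.** **A staff-level count is a coherent choice.** The hypothesis concerns staff and the bonus is paid to staff per MIBI, so the outcome matches the incentive. This stands, and is why the count should be kept.

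**Randomization and random intercepts deal with organization differences.** Half of this stands. Randomization removes bias on average from flow differences that predate allocation, as the 5.1% and 1.00 in step 3 show. A random intercept carries those differences into the standard error of an organization-level effect. It does not recover the lost precision.

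**Reversal is speculative.** This largely stands. With a fixed pool, an individual bonus discourages sharing clients among more staff. Section 5.1 places the baseline survey in month 1 and the workshops in month 2, which suggests an early roster. If added staff bring their own clients, the reversal shrinks or disappears, and so does the precision gain attributed to staff number. Even so, neither the roster date nor the date of disclosing allocation is stated.

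**Stronger readings a reader might infer.** One is that the outcome largely measures client flow. The documents give no variation in flow or delivery, and the 21% to 93% in step 2 shows that the share is undetermined. Another is that clients divided by staff caps each person's count. It caps only the organization's mean, since one person may deliver most sessions. A third is that a null result could not be told apart from differences in opportunity. That goes too far: recommended clients are recorded during the implementation phase and can be examined. Sex and race are also only examples, so other staff-level covariates are not excluded.

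**Conclusion.** The point holds as one of precision and interpretability. The plan leaves client flow per staff member out of both the consistency outcomes and their model, and in a trial of 30 organizations that variation widens the standard error of the P4P effect.

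The size depends on quantities the documents do not give. Under the assumptions in step 4, a caseload proxy of moderate quality lowers the standard error by roughly 13% to 31%. No power figure is offered, because nothing in the plan anchors one.

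The documents do not show bias. It would require staff numbers to respond to allocation, and the 12.0 to 9.6 example also requires a fixed client pool. The plan neither excludes nor establishes such a response. The change is worth making because it is cheap and closes that route.

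**What to change.** Keep the count as the outcome and make three changes.

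1. Fix and record each organization's MIBI staff roster before its allocation is disclosed, and analyse that roster.
2. In the primary model for both consistency outcomes, add as a fixed organization-level covariate the log of (adult clients with HIV served in the 12 months before enrolment ÷ rostered MIBI staff).
3. For the implementation phase, report by organization MIBIs delivered ÷ clients for whom a MIBI was recommended, as a named supporting outcome. It should not be the primary offset, because P4P may change enrolment and so the denominator. Since recruitment is described only for the implementation phase, this ratio may have no denominator in the sustainment phase, and the plan should say so.

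Cost: one caseload figure and one roster date per organization, some wording in section 10, and one degree of freedom among 30 organizations. The initial assessments that item 3 needs are already collected.

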2.3 Client outcomes

The SAT2HIV-II Project's three client outcomes are:

Days using primary substance: The number of days clients used their primary substance (i.e., the substance the client identified a willingness to talk about during the MIBI) during the past 28 days, collected via the Addiction Severity Index—Lite.⁶⁴

Anxiety: The sum of the 7 items included in the Generalized Anxiety Disorder (GAD-7) instrument.⁶⁵ Bahorik and colleagues (2016)⁶⁶ found reductions in substance use to be associated with reductions in anxiety as measured by the GAD-7.

Depression: The sum of the 8 items included in the Patient Health Questionnaire (PHQ-8) instrument.⁶⁷ Bahorik and colleagues (2016)⁶⁶ found reductions in substance use to be associated with reductions in depression.

3 SUBJECT SELECTION

Consistent with the goal of the funding opportunity, subjects for the SAT2HIV-II Project are limited to those from HSOs supported by HRSA Ryan White funding. Below are descriptions regarding the selection of HSO staff and client participants, the latter of which are considered a vulnerable population due to having HIV.

3.1 HSO staff

Each collaborating HSO will select their staff to be invited to participate as part of the project. Staff may participate as leadership staff or as MIBI staff.

3.2 HSO clients

All HSO clients who have been diagnosed with HIV and are 18 years of age or older will be invited to participate in the project.

4 INFORMED CONSENT

4.1 HSO staff

A participation agreement, memorandum of understanding, and/or subgrant will be executed between RTI International and each of the project's collaborating HSOs. Each collaborating HSO will select staff to be invited to participate in the project, and all staff must give their informed consent to participate. The project's RTI-based research staff will send each identified staff member an email with a link to the online informed consent. Both the email and the informed consent will emphasize that participation in the project is voluntary and to contact [name] by [contact]) or email ([contact]) if they have any questions or concerns.

4.2 HSO clients

During the project's implementation phase, we will seek to inform all HSO clients who have been diagnosed with HIV and are 18 years of age or older about the research project. A copy of the project's participant recruitment flyer will be included as part of the collaborating HSOs' pre-appointment paperwork and posted on the HSOs' bulletin boards and websites. Interested individuals may access the online informed consent via their own internet-capable device or, as described on the recruitment flyer, they may request to use one of the project's electronic tablets. As noted on the recruitment flyer and in the informed consent, individuals may call the project's toll-free number (to be determined) or email the project's email address ([contact]) with any questions or concerns they have about the project, both of which are monitored by the project's RTI-based research staff.

5 STUDY PROCEDURES

5.1 HSO staff

The expected duration of participation for each HSO staff participant is 19 months. Organized chronologically, below are the study procedures. All online staff surveys will be programmed using Voxco.

Complete baseline staff survey. During month 1, all consenting staff participants will be emailed a unique link to the project's online baseline staff survey, which will take about 25 minutes to complete. Each staff participant who completes the baseline staff survey will receive \$25 as compensation.

Complete online introduction to motivational interviewing course. During month 1, all MIBI staff participants will be emailed a link to the project's 5-hour online introduction to motivational interviewing course.

Participate in virtual motivational interviewing training workshop. During month 2, all MIBI staff participants will be emailed a Zoom training link and passcode for each of the project's three 4-hour motivational interviewing training workshops.

Complete follow-up staff survey. During month 2, after the training workshops, all MIBI staff participants will be emailed a unique link to the project's online follow-up staff survey, which will take about 25 minutes to complete. Each staff participant who completes the follow-up staff survey will receive \$25 as compensation.

Submit recording of MIBI roleplay session. Beginning in month 2, after the completion of the project's second motivational interviewing workshop training, all MIBI staff participants will be asked to submit a recording of their MIBI roleplay session that will be conducted with one of their organization's other MIBI staff participants.

Submit recordings of MIBI sessions with client participants. After demonstrating proficiency via a MIBI roleplay session, all MIBI staff participants will be asked to submit a recording for each MIBI session they implement with a client participant.

Review standardized motivational interviewing fidelity feedback reports. Each MIBI session recording will be rated for fidelity, and MIBI staff participants will be asked to review each fidelity feedback report.

Participate in MIBI consultation meetings. Beginning in month 3, all MIBI staff participants will be asked to participate in monthly 30-60-minute virtual group consultation meetings with an MI expert.

Participate in ISF meetings. Beginning in month 1, all staff participants will be asked to participate in monthly 30-60-minute virtual ISF team meetings with an implementation expert.

Complete follow-up staff surveys. At months 7, 13, and 19, all staff participants will be emailed a unique link to the project's online follow-up staff survey, which will take about 25 minutes to complete. Each staff participant will receive \$25 as compensation for each follow-up staff survey completed.

5.2 HSO clients

The expected duration of participation for each HSO client participant is about 1 day if the MIBI is not recommended based on their answers on the initial assessment or about 5 weeks if the MIBI is recommended. All online client assessments will be programmed using Voxco. For all online client assessments, client participants will access them either via a unique link that is emailed to them or by entering a unique participant ID that is emailed to them.

Complete initial assessment. All consenting client participants will be asked to complete an online initial client assessment, which will take about 10 minutes to complete. Each client participant who completes the initial client assessment will receive \$10 as compensation.

Participate in a MIBI session. Client participants for whom the MIBI is recommended will be asked to participate in a 15-30-minute MIBI session with one of the project's trained MIBI staff, which will be recorded for quality assurance purposes.

Complete pre-MIBI assessment. Client participants who participate in a MIBI session will be asked to complete an online pre-MIBI client assessment, which will take about 20 minutes to complete, immediately prior to receiving the MIBI session. Each client participant who completes the pre-MIBI client assessment will receive \$20 as compensation.

Complete post-MIBI assessment. Immediately after receiving the MIBI session, client participants will be asked to complete an online post-MIBI client assessment, which will take about 10 minutes to complete. Each client participant who completes the post-MIBI client assessment will receive \$10 as compensation.

Complete 4-week follow-up assessment. Four weeks after receiving the MIBI session, client participants will be asked to complete an online follow-up client assessment, which will take about 10 minutes to complete. Each client participant who completes the follow-up client assessment will receive \$10 as compensation. Client participants who complete the follow-up client assessment within 24 hours of being emailed their unique link will receive \$10 in bonus compensation. Client participants who complete the follow-up client assessment within 48 hours of being emailed their unique link will receive \$5 in bonus compensation.

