Secondary Aim. Analyses on the impact of the P4P strategy (i.e., ATTC+ISF+P4P compared to ATTC+ISF) on client-level outcomes will be analyzed using a three-level mixed-effects regression model (clients c nested in staff s nested in organization o), with an appropriate distributional assumption. The primary predictor will be organizational-level condition assignment (ATTC+ISF+P4P condition = 1; ATTC+ISF condition = 0), and its estimated effect is β_2 . Random intercepts β_{0so} will adjust for organization and staff differences. Random intercepts will adjust for organization and staff effects on the relationship between baseline client outcomes and the follow-up outcome β_{1so} . The basic reduced form of the model is $y_{cso(follow-up)} = \beta_{0so} + \beta_{1so}y_{cso(baseline)} + \beta_2P4P + \varepsilon_{cso}$. A sensitivity analysis will be conducted for each outcome by adding potential staff-level and client-level confounders (e.g., sex, race) to the model.

Exploratory Aim. For the exploratory aim, we will use the staff-level data and client-level data used above, as well as the average implementation climate score for each MIBI staff member (i.e., the hypothesized mediator). We will apply a Baron-and-Kenny-style mediation approach, which uses centering within context and includes a group mean at level three. Step 1 is that the outcome will be regressed on the condition variable (ATTC+ISF+P4P condition = 1; ATTC+ISF condition = 0) in a multilevel regression. Step 2 is that the outcome will be predicted by both condition and the group mean-centered mediator (i.e., implementation climate) in a multilevel regression. Step 3 is that the mediational effect will be calculated by subtracting the estimated coefficient associated with condition in Step 2 from the estimated coefficient associated with condition in Step 1. This method will allow the between-group mediation effect to be partitioned from the within-group mediation effect, which is important because between-group mediation is the effect of interest. Significance of the mediation effect will be calculated using the Freedman and Schatzkin t statistic.

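### The client analysis covers only MIBI recipients who completed the 4-week assessment, which is narrower than the blanket intent-to-treat statement and the client hypothesis suggest

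*Combined protocol and SAP*

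**What the plan says.** All references are to the combined protocol and SAP.

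- **Entry.** During the implementation phase, Section 4.2 says "we will seek to inform all HSO clients who have been diagnosed with HIV and are 18 years of age or older". Section 5.2 gives every consenting client an initial assessment, and whether a MIBI is recommended is decided "based on their answers on the initial assessment". Recommended clients are then asked to have a session.
- **Outcome collection.** Section 5.2 reserves the next assessment for those who attend: "Client participants who participate in a MIBI session will be asked to complete an online pre-MIBI client assessment". The outcome is timed from the session: "Four weeks after receiving the MIBI session, client participants will be asked to complete an online follow-up client assessment".
- **Outcome definition.** Section 2.3 defines the primary substance by what the client was willing to discuss in the MIBI. The anxiety and depression scores carry no such condition.
- **Claim.** The secondary hypothesis in Section 2.1 predicts reductions in client substance use, anxiety and depression, and does not limit them to recipients. Section 10 opens with "All analyses will follow the intent-to-treat principle".
- **Model.** Section 10, Secondary Aim, places clients within staff within organizations, adjusts for the baseline outcome, and states: "The primary predictor will be organizational-level condition assignment". A sensitivity analysis adds staff-level and client-level confounders.
- **Incentive.** Section 1.2 pays staff in the experimental arm $10 for every MIBI delivered, and a further $10 if it meets the quality benchmark.

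**The concern.** An intent-to-treat comparison rests on a group fixed by randomization. Here a client enters the analysis only by receiving a session and then completing follow-up. Both happen after organizations are randomized, and the first is what the tested strategy pays for in one arm.

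Two things are at stake. The first is scope. A result reported as P4P improving, or not improving, client outcomes would describe recipients with follow-up, not everyone for whom the MIBI was recommended. If P4P helps clients mainly by getting more of them into a session, that benefit falls outside this analysis. The second is comparability. If the two arms treat different kinds of client, part of any difference reflects who was treated. No section plans to report how many clients were recommended, treated and followed up in each arm, so a reader could not tell.

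**Working it through.** The documents state no client sample size, power, uptake or intraclass correlation, so there is no figure to reproduce. The check traces the client flow and then asks what the resulting comparison can and cannot show.

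**1. Who has an outcome.** Consent, initial assessment, recommendation, session, 4-week assessment (Section 5.2). The last step is dated from the session, and no other outcome date is given. A recommended client without a session therefore has no 4-week value. Two other places agree: the Section 2.3 substance definition needs a MIBI, and the Section 10 model needs a staff member for each client. The analysed set is recipients who completed follow-up.

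**2. Set against the claims.** Analysis by assigned condition is planned, so that part of intent-to-treat holds. No section defines the client set, and neither Section 2.1 nor the opening of Section 10 limits it to recipients.

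**3. What the comparison cannot see.** Let p0 and p1 be the shares of recommended clients treated under control and P4P, and m the benefit of one MIBI, equal in both arms. If P4P only widens reach and the added recipients are otherwise similar:

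- effect among all recommended clients = m × (p1 − p0)
- difference among recipients = 0

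With assumed reach of 40% and 60%, the first is m × (0.60 − 0.40) = 0.20m and the second is still 0.

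**4. Whether the mix must differ.** Suppose half of recommended clients are ready to change and half are not, with the same recommended pool in both arms. The ready share among recipients is r/(r + n), where r and n are the reach in each half. Every row below raises overall reach from 40% to 60%; all inputs are assumed.

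| Control, ready/not | P4P, ready/not | Ready share, control | Ready share, P4P | Difference |
|---|---|---|---|---|
| 60/20% | 80/40% | 60/80 = 0.750 | 80/120 = 0.667 | −0.083 |
| 40/40% | 60/60% | 40/80 = 0.500 | 60/120 = 0.500 | 0 |
| 40/40% | 80/40% | 40/80 = 0.500 | 80/120 = 0.667 | +0.167 |
| 60/20% | 90/30% | 60/80 = 0.750 | 90/120 = 0.750 | 0 |

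Any spurious difference is the last column times the gap in mean outcome between the two kinds of client. The same rise in reach can push it either way or leave it at zero. The table shows that direction is open; it says nothing about size in this trial.

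**5. What the planned adjustments reach.** Baseline adjustment deals with selection acting through the baseline value. The baseline appears to be the pre-MIBI assessment, but Section 10 does not say so. The confounder sensitivity analysis deals with other measured differences. Both act within recipients who have a follow-up value; neither touches unmeasured factors or the clients who have no outcome.

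**The case against.** **Intent-to-treat is respected, because organizations are randomized and clients are analysed as assigned.** This stands as far as it goes. A reader might infer that the plan breaks its own rule. The documents do not support that: Section 10 never defines the client set. The fault is a statement broader than the analysis.

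**The restriction is already implied.** For substance use it is, through Section 2.3 and the model's nesting. The anxiety and depression definitions carry no such limit, and Sections 2.1 and 10 state none.

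**Differential receipt is only inferred.** This stands. It is tempting to say that the trial itself expects P4P to reach a larger share of recommended clients. Sections 2.1 and 2.2 hypothesize a higher number of MIBIs per staff member. That number can rise because more clients consent and are screened, with the share unchanged. Differences could then arise before recommendation, so the flow should be reported from consent.

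**The plan has safeguards.** It does: broad invitation, a recommendation resting on the client's own answers, baseline adjustment, the confounder sensitivity analysis, and payment with bonuses for prompt follow-up. The first two limit staff discretion up to the recommendation, but not over who then has a session.

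**Two side issues should not be added to this point.** The expected duration of "about 5 weeks if the MIBI is recommended" might be read as promising follow-up to everyone recommended. It is an approximate duration that presumes uptake, and it changes nothing. Section 10 also announces "below are descriptions of the sample size, missing data, power, and analysis plan" and gives no missing-data description for this aim. That leaves recipients lost before four weeks without stated handling, but the gap affects every aim and is a separate matter.

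**Conclusion.** The point holds as one of scope, with a possible but unproven bias. As planned, the secondary analysis compares recipients who completed the 4-week assessment, by assigned condition. It can show an effect of better MIBI delivery among them; it cannot show client benefit from treating more of those recommended. The intent-to-treat statement and the client hypothesis should be narrowed to match.

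A reader might go further and conclude that the client comparison is biased by some number of days of use. The documents do not support that. They give no uptake, client numbers or spread of outcomes, and assumed inputs lead to shifts in either direction or none.

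The scope conclusion rests on the text alone. The possibility of bias rests on receipt following randomization and being paid for in one arm. The primary aim is unaffected: its outcomes are measured on staff, and the number of MIBIs is one of them. This should be fixed, because a headline secondary conclusion would otherwise be wider than its data.

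**What to change.** In Section 10, Secondary Aim, with Section 2.1 and the opening of Section 10 matched to it:

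1. State that client outcomes are compared by assigned condition among clients who received a MIBI and completed the 4-week assessment, that conclusions are limited to this group, and that the result is not an intent-to-treat effect on all recommended clients. Name the assessment that supplies the baseline.
2. Report by arm the numbers who consented, completed the initial assessment, were recommended a MIBI, received one, and completed follow-up. Tabulate the available initial-assessment characteristics of recommended clients with and without a MIBI.
3. Choose the client-level covariates of the planned sensitivity analysis from the initial assessment where available.

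Items 1 and 2 cost wording and tabulation. Item 3 specifies an analysis already planned and depends on what the initial assessment holds, which the documents do not describe. The main model is unchanged.

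Weighting for receipt and follow-up completion is an optional addition. It widens intervals. For receipt alone, take the first row of the table with weights w = 1/reach; the effective sample fraction is (mean w)² / mean(w²).

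- Control: 2.5² / 8.33 = 0.75, so the standard error is multiplied by 1/√0.75 = 1.15.
- P4P: 1.667² / 3.125 = 0.89, so the multiplier is 1.06.
- Difference, with equal recipients per arm: √((1/0.75 + 1/0.889)/2) = 1.11.

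These figures use assumed reach, ignore clustering, and suppose that the selecting factor was measured. Weighting does not correct for unmeasured factors or recover the effect of wider reach. Following up every recommended client would be a larger design change and is not asked for here.
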